8.2 RESPONSIBILITY FOR ANALYSES/IN-HOUSE BLINDING

The statistical analyses of the data obtained from this study will be the responsibility of the Clinical Biostatistics department of the SPONSOR.

This study will be conducted as a double-blind study under in-house treatment blinding procedures. The central laboratory values for NT-pro BNP will also be blinded after Visit 2. The official, final database will not be unblinded until medical/scientific review has been performed, protocol violators have been identified, and data have been declared final and complete.

The Clinical Biostatistics department will generate the randomized allocation schedule(s) for study treatment assignment. Randomization will be implemented in an interactive voice response system (IVRS).

8.3 Hypotheses/Estimation

Objectives and hypotheses of the study are stated in Section 3.0 – Objectives & Hypotheses

8.4 Analysis Endpoints

Efficacy and safety endpoints that will be evaluated are listed below.

8.4.1 Efficacy Endpoints

Primary Endpoint

The primary endpoint of the study is the time to the first occurrence of the composite endpoint of CV death or HF hospitalizations. Subjects without a HF hospitalization or CV death at the time of analysis will be censored at time of non-CV death or time of last information available during the pre-specified follow-up period for subjects still alive at time of analysis. Only clinical events confirmed by CEC will be used to define the primary endpoint.

Secondary Endpoints

The secondary study endpoints are:

- Components of the primary composite endpoint:
 - Time to CV death
 - Time to first HF hospitalization
- Time to total HF hospitalizations (first and recurrent)
- Time to first occurrence of the composite of all-cause mortality or HF hospitalization
- Time to all-cause mortality

Exploratory Endpoints

The following endpoints will be considered outside of the testing procedure and considered as exploratory endpoints:

- Time to first HF event, defined as composite of HF hospitalization or urgent HF visit (not meeting the criteria for a HF hospitalization).
- Time to first CV hospitalization
- Total number of HF hospitalizations
- Change from baseline in health-related quality of life measures (KCCQ and EQ-5D)

8.4.2 Safety Endpoints

Safety measurements are described in Section 7.0 – Trial Procedures

8.4.3 Clinical Events Committee (CEC)

A clinical events committee (CEC) will be created to review and adjudicate each suspected clinical endpoint event without unblinding treatment. The CEC will comprise qualified members, who are not investigators in the study and not otherwise directly associated with the sponsor. The CEC members will remain blinded to treatment throughout the adjudication process and the study. The adjudication guidance and clinical endpoint event definitions will be described in detail in the CEC charter. Only clinical endpoint events adjudicated by the CEC will be used in the final efficacy and safety analyses.

Analysis of CEC adjudicated clinical events not already pre-specified as the primary, secondary or exploratory endpoints will be described in the supplemental Statistical Analysis Plan (sSAP).

8.5 Analysis Population

The primary endpoint analysis will use the Intention-to-Treat (ITT) population. The ITT population includes all randomized subjects. The subjects will be analyzed according to the planned treatment. Subjects without any post-randomization information will be censored at Day 1.

The ITT population will also be used for the secondary and exploratory efficacy endpoints analyses. The subjects will be analyzed according to the planned treatment. Subjects without any post-randomization information will be censored at Day 1 for time to event endpoints.

The All-Subjects-as-Treated (ASaT) population will be used for safety analyses. The ASaT population includes all subjects who have taken at least one dose of study drug (vericiguat or placebo). All subjects will be analyzed according to the actual treatment received. Any subjects in ASaT who received both placebo and vericiguat during the study by mistake will be analyzed according to the planned treatment.

8.6 Statistical Methods

8.6.1 Statistical Methods for Efficacy Analyses

Efficacy results will be deemed to be statistically significant after consideration of the Type I error control strategy as described in Sections 8.7 and 8.8. A brief summary of analysis

approaches for the primary and secondary efficacy endpoints are described in [Table 7](#). Nominal p-values will be computed for other efficacy analyses, but should be interpreted with caution due to potential issues of multiplicity.

Analysis of Primary Endpoint

The analysis of the primary efficacy endpoint will follow the intention-to treat principle and will be performed in the ITT population, comprised of subjects randomized. Subjects will be analyzed as randomized. The analysis of the primary endpoint will be based on results from adjudication and will test if the time to the first occurrence of the composite endpoint is prolonged in the MK-1242 (vericiguat) treatment group. Randomized subjects without any HF hospitalization or CV death event at the time of analysis will be censored at their last available information or the date of their non-CV death.

The analysis will be performed with a one-sided log-rank test, stratified by the same six strata by region and race that are considered for randomization, testing the following null hypothesis:

$$H_0: S_{Vericiguat}(t) = S_{Placebo}(t) \quad \text{for all time points } t \geq 0.$$

The alternative hypothesis will be:

$$H_1: S_{Vericiguat}(t) > S_{Placebo}(t) \quad \text{for at least one time point } t \geq 0 \text{ and} \\ S_{Vericiguat}(t) \geq S_{Placebo}(t) \quad \text{for all time points } t \geq 0.$$

$S_{Vericiguat}$ denotes the (event-free) survival function of the vericiguat treatment group and $S_{Placebo}$ denotes the (event free) survival function of the placebo treatment group.

The overall study-wise one-sided type I error rate will be controlled at 0.025. The following decision rule to test the null hypothesis will be applied:

If the z-value from the one-sided stratified log-rank test (for the difference $S_{Vericiguat} - S_{Placebo}$) is larger than the critical quantile from the standard normal distribution ($z_{1-\alpha}$, with α being the nominal significance level at the respective interim or final analysis), the null hypothesis will be rejected in favor of the alternative hypothesis.

Kaplan-Meier estimates of the primary composite endpoint (95% confidence interval) survival curves will be presented for each treatment group. Hazard ratio, relative risk reduction and corresponding 95% confidence intervals will be estimated based on a Cox proportional hazards model stratified by the same factors as used for the primary efficacy analysis.

The number and proportion of subjects with a CV death or HF hospitalization event will be provided by treatment group. In addition, rates per 100 patient-years will be provided.

Analysis of Secondary Endpoints

Analogous to the analysis of the primary endpoint, the analysis of the secondary efficacy endpoints will be performed under the intention to treat principle. All subjects randomized will be included in the analysis. Subjects will be analyzed as randomized.

A one-sided stratified log-rank test similar to the one used for the primary efficacy endpoint will be used to test if the time to first HF hospitalization, time to CV death, time to all-cause mortality, and time to first occurrence of the composite of all-cause mortality or HF hospitalization is prolonged in the vericiguat treatment group compared to placebo.

The time-to total HF hospitalization will be tested with an Andersen-Gill model [14] to compare the vericiguat treatment group to placebo. The Anderson-Gill model is an extension of the Cox proportional hazards model, where the hazard for the kth event, i.e. including both first and recurrent, for a subject i at time t, is given by

$$h_{ik}(t) = h_0(t) \exp(\beta T x),$$

with $h_0(t)$ being the baseline hazard and x the vector of covariates for subject i.

Treatment group and the stratification factors used for randomization will be included in the model as fixed effects. Robust standard errors will be used to account for correlations of event times within a subject [15] [16].

The following null hypothesis will be compared with the alternative hypothesis:

$$H_0: \quad HR_{\text{Vericiguat/Placebo}} = 1$$

$$H_1: \quad HR_{\text{Vericiguat/Placebo}} < 1$$

Superiority of MK-1242 (vericiguat) over placebo in prolonging the time to total HF hospitalization will be concluded, if the upper limit of the confidence interval of the hazard ratio is below 1 with the confidence level matching the nominal alpha level used for testing at the interim or final analysis. Estimates of treatment comparisons and effect size including 95% confidence intervals will be provided based on the fitted model.

In addition, time to total HF hospitalizations and CV death will be analyzed using the Wei, Lin, Weissfeld (WLW) method [17], and details will appear in the supplemental SAP.

Missing Data

Subjects who prematurely withdraw from study treatment will be followed for further data collection. As long as the subject does not withdraw consent for any further data collection, every effort will be made to collect at least data on the components of the primary endpoint up to the last safety phone call which occurs two weeks after the final study visit. Subjects are requested to attend the protocol specified study visits. If a subject does not attend the regular study visits, the investigator will contact the subject via telephone to collect at least data for the primary endpoint.

Due to this follow up approach, it is expected that the amount of missing data will be only minor, as most subjects will be followed up until trial termination.

For the primary analysis, subjects without any HF hospitalization or CV death event at the time of analysis will be censored at their last available information or the date of their non-CV death. The censoring mechanism is assumed to be non-informative.

Supportive analyses will be performed to assess the impact of a potential informative censoring and missing data, and details will be described in the supplemental statistical analysis plan.

Table 7 Primary Analysis Strategy for Efficacy Variables

Endpoint/Variable	Statistical Method [†]	Analysis Population	Missing Data Approach
Primary Hypothesis:			
Time to first occurrence of the composite endpoint of CV death or HF hospitalization	Stratified Log-Rank Test	ITT	Censored at the last available information
Secondary Endpoints:			
Time to the first occurrence of CV death	Stratified Log-Rank Test	ITT	Censored at last known alive date
Time to the first occurrence of HF hospitalization	Stratified Log-Rank Test	ITT	Censored at the last available information
Time to total HF hospitalizations (including the first and recurrent events)	Andersen-Gill model [‡]	ITT	Censored at the last available information
Time to first occurrence of the composite of all-cause mortality or HF hospitalization	Stratified Log-Rank Test	ITT	Censored at last available information
Time to all-cause mortality	Stratified Log-Rank Test	ITT	Censored at last known alive date
[†] Statistical models are described in further detail in the text. For stratified analyses, the stratification factors used for randomization will be used as stratification factors for analysis. [‡] Treatment group and the stratification factors used for randomization will be included in the model as fixed effects.			

8.6.2 Statistical Methods for Safety Analyses

Safety and tolerability will be assessed by clinical review of all relevant parameters including adverse events (AEs), laboratory tests, and vital signs.

The analysis of safety results will follow a tiered approach (Table 8). The tiers differ with respect to the analyses that will be performed. Safety parameters or adverse events of special interest that are identified a priori constitute “Tier 1” safety endpoints that will be subject to inferential testing for statistical significance with p-values and 95% confidence intervals provided for between-group comparisons. Other safety parameters will be considered Tier 2 or Tier 3. Tier 2 parameters will be assessed via point estimates with 95% confidence intervals provided for between-group comparisons; only point estimates by treatment group are provided for Tier 3 safety parameters. P-values (Tier 1 only) and 95% confidence intervals (Tier 1 and Tier 2) will be provided for between-treatment differences in the percentage of subjects with events; these analyses will be performed using the unstratified Miettinen and Nurminen method.

Adverse events (specific terms as well as system organ class terms) and predefined limits of change in laboratory and vital signs that are not pre-specified as Tier-1 endpoints will be classified as belonging to "Tier 2" or "Tier 3", based on the number of events observed.

Membership in Tier 2 requires that at least 4 subjects in at least one treatment group exhibit the event; all other adverse events and predefined limits of change will belong to Tier 3.

The threshold of at least 4 events was chosen because the 95% confidence interval for the between-group difference in percent incidence will always include zero when treatment groups of equal size each have less than 4 events and thus would add little to the interpretation of potentially meaningful differences. Because many 95% confidence intervals may be provided without adjustment for multiplicity, the confidence intervals should be regarded as a helpful descriptive measure to be used in review, not a formal method for assessing the statistical significance of the between-group differences in adverse events and predefined limits of change.

Continuous measures such as changes from baseline in laboratory and vital signs that are not pre-specified as Tier-1 endpoints will be considered Tier 3 safety parameters. Summary statistics for baseline, on-treatment, and change from baseline values will be provided by treatment group in table format. In addition, summary statistics for the difference between treatment groups will also be provided, along with nominal p-values for between-group differences. Mean change from baseline over time will be plotted with the corresponding standard errors.

Table 8 Analysis Strategy for Safety Parameters

Safety Tier	Safety Endpoint [†]	p-Value	95% CI for Treatment Comparison	Descriptive Statistics
Tier 1	
 • Syncope • Symptomatic hypotension 	X	X	X
Tier 2	
 Any AE Any Serious AE Any AE leading to death Any Drug-Related AE Any Serious and Drug-Related AE Discontinuation due to AE Specific AEs, SOCs, or PDLCs[‡] (incidence \geq4 of subjects in one of the treatment groups) 		X	X
Tier 3	
 Specific AEs, SOCs or PDLCs[‡] (incidence $<$4 of subjects in all of the treatment groups) Change from Baseline Results (Labs, Vital Signs) 			X

[†] Adverse Event references refer to both Clinical and Laboratory AEs.
[‡] Includes only those endpoints not pre-specified as Tier 1 or not already pre-specified as Tier-2 endpoints.
 Note: SOC=System Organ Class; PDLC=Pre-Defined Limit of Change; X = results will be provided.

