- k. Dose assessment based on criteria described in Section 5.2.1.2.
- l. Complete physical exam completed at Visit 2. Directed physical exams to be completed at Week 48 (Visit 7), subsequent Yearly visits, and the Premature Discontinuation Visit and/or Final Visit.
- m. Three measurements, each approximately 2 min apart. Visit 2: Prior to and at 2 ±0.5h post study-drug dosing; Visit_n until Final visit: vital sign measurement is only needed prior to study drug dosing. Blood Pressure and pulse rate measurements should be performed as described in Appendix 12.5
- n. This assessment can be performed at any point in the trial when vital status is in question.
- o. Local laboratory creatinine and NT-proBNP or BNP within 30 days before randomization will be entered in eCRF to confirm eligibility. The creatinine assessed at this time will be used to calculate eGFR by MDRD equation. Recent historical local laboratory assessments may be used provided these assessments were obtained within 30 days before randomization.
- p. NT-proBNP measurements assessed by the central lab will be blinded after Visit 2.
- q. Hemoglobin A1c to be evaluated in diabetic subjects only.
- r. In case of positive urine pregnancy test, a confirmatory serum test will be done. A negative result is required for randomization.
- s. Refer to section 7.1.3.4 for sample collection information.
- t. In case the PK sample at the specified visits cannot be obtained at a specified time point, the sample can be taken at the subsequent visits within the year of treatment. Exact collection date/time of the

Trial Period	Screening		Treatment								Premature Treatment Discontinuation ^f		
	1 Screen ^a	2 Rand ^b	3	4	5	6	7	Visit ⁿ ^c	Final Visit ^d	Final Phone Contact ^e	Discon Visit ^g	Safety Follow-up Visit ^h	Cont. through end of trial ⁱ
Visit Number/Title:	Day -30 to -1	Day 1	Day 14	Day 28	Week 16 (Month 4)	Week 32 (Month 8)	Week 48 (Month 12) and Yearly ^j	Every 16 weeks	At time of Efficacy Cut-off	14 days after Final Visit	At time of permanent treatment discon	14 days from last dose	Every 16 weeks
Scheduled Days/Week/Month:													
Scheduling Window Days/Weeks/Months:			±4 days	±4 days	±2 weeks	±2 weeks	±2 weeks	±2 weeks		+1 week		+1 week	±2 weeks

PK samples and date/time of last study drug intake (either at home on the day before the sample or at site) must be documented.

- u. Not applicable for subjects who prematurely discontinue from study treatment.

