7.1.2.3 Physical Examinations

The investigator or qualified designee will perform a full physical exam at the time of randomization. Clinically significant abnormal findings should be recorded as medical history.

Directed physical exams with a focus on cardiovascular assessment will be performed at the yearly visits and at the Premature Discontinuation Visit and/or Final Visit.

7.1.2.4 12-Lead Electrocardiogram

Electrocardiograms (ECG) will be obtained as described in the Trial Flow Chart-Section 6.0.

- Subjects will refrain from nicotine-containing products and/or ingesting caffeine for at least 30 minutes preceding the procedure.
- 12-lead ECGs should be performed after the subject has rested quietly for approximately 10 minutes.

Record ECG with a paper speed of 25 mm/sec. Ensure standard calibration is performed and provide record of a calibration mark indicating the equivalence of 1mV signal to 10 mm vertical deflection on the ECG. The same ECG machine should be used at all time points for an individual subject.

At each scheduled ECG assessment, sites should print 2 original paper tracings. One original paper tracing should be maintained in subject files and the second original paper tracing should be mailed to the core ECG vendor (batched once monthly).

These ECGs will be used to assess the impact of study drug on electrocardiographic changes such as heart rate and repolarization.

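### Section 8.6.2 plans between-group differences in laboratory and vital-sign changes without stating any baseline adjustment; ANCOVA on the baseline already collected would be more precise at almost no cost

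*Combined protocol and SAP*

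**What the plan says.** Section 8.6.2 places these measures in the lowest safety tier: "Continuous measures such as changes from baseline in laboratory and vital signs that are not pre-specified as Tier-1 endpoints will be considered Tier 3 safety" measures. It then describes the output. First, "Summary statistics for baseline, on-treatment, and change from baseline values will be provided by treatment group in table format". Next, "In addition, summary statistics for the difference between treatment groups will also be provided, along with nominal p-values for between-group differences". Mean change over time is also to be plotted with standard errors. No test, model or covariate is named for the between-group difference.

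Earlier in the same section the general rule for this tier is narrower: "only point estimates by treatment group are provided for Tier 3 safety parameters". P-values are reserved there for Tier 1, and confidence intervals for Tiers 1 and 2. Table 8 agrees with that rule: for Tier 3, including laboratory and vital-sign changes, it marks descriptive statistics only.

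The one comparison method that 8.6.2 does name concerns percentages of subjects with events: "these analyses will be performed using the unstratified Miettinen and Nurminen method". It does not apply to continuous changes.

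Baseline values exist. The Trial Flow Chart schedules central hematology and chemistry at Visit 2, and its vital-signs footnote reads "Visit 2: Prior to and at 2 ±0.5h post study-drug dosing".

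**The concern.** A difference in mean change subtracts the whole baseline value from each follow-up value, which amounts to fixing the baseline slope at 1. Unless that happens to be the right slope, the estimate carries avoidable noise. With equal standard deviations and r below 1, the change score over-corrects: an arm that starts higher by chance tends to show a larger fall for that reason alone. ANCOVA estimates the slope from the data and removes this.

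The size of the systolic pressure effect will be read closely, because titration is guided by systolic pressure (section 5.2.1.2). A nominal p-value with no named method also leaves the analyst to choose the model, possibly after unblinding. And because 8.6.2 promises a p-value in one place and rules it out for Tier 3 in another, two programmers could produce different tables from the same section.

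**Working it through.** **Plan's own figure.** There is none to reproduce. The documents give no standard deviation, correlation, standard error or power for any laboratory or vital-sign change.

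**Inputs.** About 4872 subjects randomized 1:1 (sections 2.1 and 5.3), so n is about 2436 per arm. This is an upper limit, since some subjects will lack a follow-up value. Assumed, because the documents are silent: the correlation r between baseline and follow-up, and equal standard deviations s at both times.

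**Formulas.**
- Raw change: Var = 2 × 2(1 − r)s²/n.
- ANCOVA: Var = 2(1 − r²)s²/n.
- SE ratio, ANCOVA to raw change: √[(1 − r²)/(2(1 − r))] = √[(1 + r)/2], whatever n is.

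**Results (in units of s, n = 2436 per arm).**

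| assumed r | SE, raw change | SE, ANCOVA | reduction |
|---|---|---|---|
| 0.3 | 0.0339 | 0.0273 | 19.4% |
| 0.5 | 0.0287 | 0.0248 | 13.4% |
| 0.7 | 0.0222 | 0.0205 | 7.8% |
| 0.8 | 0.0181 | 0.0172 | 5.1% |
| 0.9 | 0.0128 | 0.0125 | 2.5% |

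A simulation with 2436 per arm and 1500 runs gave reductions of 17.1% at r = 0.3 and 7.8% at r = 0.7. The Monte Carlo error of the first is about 0.806 × √(0.35/1500) = 0.012, so 17.1% is within two standard errors of 19.4%.

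**Unequal standard deviations.** With k the ratio of follow-up to baseline SD, the SE ratio is √[k²(1 − r²)/(1 + k² − 2rk)]. At r = 0.3, 0.5 and 0.7 the reduction is 11.4%, 5.5% and 1.0% for k = 1.25, and 29.1%, 24.4% and 20.8% for k = 0.8. The direction does not depend on k: (1 + k² − 2rk) − k²(1 − r²) = (1 − rk)², which cannot be negative.

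**Precision and imbalance are one gain.** With equal SDs, 2(1 − r) = (1 − r²) + (1 − r)². The last term is the contribution of chance baseline imbalance to the raw comparison. At r = 0.5: 0.0287² − 0.0248² ≈ 0.00021, and (1 − 0.5)² × 2/2436 ≈ 0.00021. Over repeated randomizations, removing imbalance is the whole of the gain.

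**Size of the imbalance.** Its standard deviation is √(2/2436) = 0.029 s, so 95% of trials fall within ±0.056 s. At that limit the raw comparison shifts by (1 − r) × 0.056 s, which is 0.039, 0.028 and 0.017 s at r = 0.3, 0.5 and 0.7.

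**On a blood-pressure scale.** If s were 15 mmHg (an assumption) and r = 0.5, the SE would go from 0.0287 × 15 = 0.43 to 0.0248 × 15 = 0.37 mmHg.

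**The case against.** The strongest reply is that 8.6.2 is silent rather than wrong. A treatment difference with a p-value could come from a baseline-adjusted model, and section 8.0 provides a supplemental SAP, not available here, for changes to non-confirmatory analyses. This stands in part: a reader might infer that the plan prescribes raw differences, and it does not say so. But the paragraph mentions only simple summaries. Section 8.6.1 names covariates where it wants them, as in the Andersen-Gill model. The plan also defers to the supplemental SAP by name for other items (the WLW analysis, informative censoring, other adjudicated events, evolving background therapy) and not for this one. Followed as written, it yields an unadjusted comparison.

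The second reply is that the stake is small. That stands fully. These are Tier 3 measures with nominal p-values, outside the multiplicity scheme. The pre-specified safety questions, syncope and symptomatic hypotension, are Tier 1 incidence endpoints and are untouched.

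The third reply is that adding an interval to Tier 3 contradicts the tier rules. That stands too, but those rules already conflict with the nominal p-values, so the passages must be reconciled in any case.

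A reader might extend the point to quality of life and ECG. Neither extension carries it. Section 8.4.1 lists "Change from baseline in health-related quality of life measures (KCCQ and EQ-5D") as an endpoint, not a method, and a change endpoint is compatible with ANCOVA; section 7.1.6.2 also refers to a separate analytical plan covering patient-reported outcomes. For ECG, section 7.1.2.4 says "These ECGs will be used to assess the impact of study drug on electrocardiographic changes such as heart rate and repolarization", and Table 8 has no ECG row, but that is a missing listing and has no bearing on baseline adjustment.

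**Conclusion.** The point holds as a low-severity improvement. Section 8.6.2 promises between-group differences and nominal p-values for continuous laboratory and vital-sign changes, states no baseline adjustment, and is naturally read as an unadjusted comparison of change. ANCOVA on baseline values already in hand is at least as precise in large samples and usually more so.

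The size is conditional. A reader might take 8 to 19% as a property of this trial; it holds only for r between 0.3 and 0.7 with equal standard deviations, and the documents support neither assumption. Stable measures with r of 0.8 to 0.9 would gain about 3 to 5%, and unequal standard deviations move the figure in either direction. Nor should lower standard error and protection against chance imbalance be counted as two benefits. No primary, secondary or Tier 1 conclusion depends on this.

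The conflict inside 8.6.2 over what Tier 3 reports needs no assumption: it is visible in the text and in Table 8.

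**What to change.** In 8.6.2, state that between-group differences in continuous laboratory and vital-sign measures will be estimated by ANCOVA at each scheduled visit, or by a repeated-measures model over the scheduled visits, with treatment, baseline value and the six randomization strata. Report the adjusted difference with a 95% CI, and keep the raw by-arm summaries beside it. Choose one model and fix it before unblinding; section 8.0 allows non-confirmatory changes to be recorded in the supplemental SAP.

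In the same edit, amend the general Tier 3 rule and the rule reserving p-values for Tier 1, and mark Table 8 to match (a footnote for continuous changes would do), so that the section says one thing about Tier 3 output.

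The cost is a few sentences and routine programming. It needs no new data, visits or subjects.
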